14.3.3 Vital Signs

Vital signs (systolic blood pressure, diastolic blood pressure, pulse rate, and temperature) will be summarized descriptively at each time-point using both absolute values and change from baseline for all post-baseline timepoints. The baseline value will be any measurements taken during the Baseline Period. If the Baseline Period measurements are missing, then measurements taken at screening will be used as baseline. If a patient had re-enrolled, all data gathered will be summarized (using baseline values as determined in [section 16.1](#)).

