## **6.4 Vital Signs**

Vital signs (BP and pulse rate) will be recorded on the eCRF at Screening, Study Visit 2, Study Visit 3, Study Visit 4, and at the End-of-Study Visit. Weight will be recorded at Screening and at the End-of-Study Visit. Blood pressure is to be measured with an appropriate cuff size after the patient has been sitting for at least 5 minutes.

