### **8.5 Each Treatment Day**

Patients will set up and complete a treatment using the AMIA APD Solution Generation System according to their prescribed dialysis regimen.

The following assessments will be completed each day throughout the Study Treatment Period.

1. Collection of concomitant medication information.
  2. Weight pre- and post-dialysis.
  3. Vital signs, before and after each treatment, including seated BP, pulse rate and temperature.
  4. Collection of AEs/ SAEs.
  5. Collection of ADEs and SADEs once the patient is connected to the AMIA APD Solution Generation System.
  6. Collection of AMIA APD Solution Generation System-related PCs/ DDs, which would include functional characteristics (e.g., particulate matter, PD fluid discoloration, leaks, tubing separations), will begin from the time of signing informed consent and will continue throughout the entire Study Treatment Period.
  7. Collection of machine information.
  8. Collection of machine observations.
  9. Chlorine testing performed by patients before each treatment.
- 
- 

10. Collection of diary source data (eDiary).

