## **10. PLANNED STATISTICAL METHODS**

### **10.1 General Considerations**

Further details of the planned statistical methods will be provided in the study SAP. The SAP will be finalized prior to database lock. Any changes to the statistical methods described in the protocol will be documented in the SAP.

Unless otherwise noted, all analyses will be performed using SAS/GRAPH® 9.4 software, SAS/STAT® 14.1 software and Base SAS® 9.4. Copyright© 2002-2012, SAS Institute Inc. SAS and all other SAS Institute Inc. product or service names are registered trademarks or trademarks of SAS Institute Inc., Cary, NC, USA. All Rights Reserved.

Summary statistics will be presented with mean, standard deviation, median, minimum and maximum for continuous variables and frequency count and percentage based on study population will be used to summarize categorical variables. Prior to analysis, data will be reviewed for consistency. Missing data values will not be imputed and all non-missing values will be used. To determine patients who had been re-enrolled in the study, there will be a question on the eCRF indicating whether the patient has been enrolled in the trial previously and the number the patient was previously enrolled under. The details on how data from these patients will be analyzed will be described in the SAP.

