### **10.2 Determination of Sample Size**

A formal sample size calculation was not performed. Up to 50 patients will be enrolled such that a total target of 30 evaluable patients complete the 12-week Study Treatment Period and the Follow-up Period.

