## **10.6 Secondary Analysis**

Adverse events will be mapped to a Primary System Organ Class and Preferred Terms according to MedDRA Version 21.0 or higher and summarized using frequencies and percentages. In addition, AEs will be summarized by seriousness, severity, and relationship to study product or typical PD therapy. Device alarms and their relation to AEs or SAEs will be summarized using frequency counts and percentages. Vital Signs (BP, pulse, temperature) will be summarized by mean, standard deviation, median, minimum and maximum for all recorded timepoints and also for change from pre-to post treatment for all post Baseline timepoints. These summaries will be conducted on the Safety Set.

Total  $Kt/V_{\text{urea}}$  will be summarized using descriptive statistics at all collection timepoints and change from Baseline will also be summarized. This summary will be performed on the Safety Set.

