12. CHANGES IN PLANNED ANALYSES FROM THE PROTOCOL

There have been no changes from the planned analyses in the protocol.

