17. LIST OF TABLES, FIGURES AND LISTINGS

Table Number	Table Name
14.1.1	Patient Overview
14.1.2	Patient Disposition
14.1.3	Protocol Deviations Summary
14.1.4	Categorical Demographic and Baseline Characteristics
14.1.5	Continuous Demographic and Baseline Characteristics
14.2.1	Overall Testing of the Chemical Composition of the Dialysis Solution (Primary Efficacy Endpoint)
14.2.2	Individual Parameter Testing of the Chemical Composition of the Dialysis Solution
14.2.3	Individual Parameter Summary of the Chemical Composition of the Dialysis Solution
14.2.4	Total Kt/V _{urea} Summary (Secondary Efficacy Endpoint)
14.2.5.1	eDiary Treatment Summary
14.2.5.2	Treatment Interruptions Summary
14.3.1.1.1	Summary of Adverse Events
14.3.1.1.2	Treatment-Emergent Adverse Events by SOC and Preferred Term
14.3.1.1.3	Serious Treatment-Emergent Adverse Events by SOC and Preferred Term
14.3.1.1.4	Treatment-Emergent Adverse Events Related to Study Device by SOC and Preferred Term
14.3.1.1.5	Treatment-Emergent Adverse Events Related to Typical PD Therapy by SOC and Preferred Term
14.3.1.1.6	Treatment Emergent Adverse Events Related to Another Baxter Product by SOC and Preferred Term
14.3.1.1.7	Serious Treatment-Emergent Adverse Events Related to Study Device by SOC and Preferred Term
14.3.1.1.8	Serious Treatment-Emergent Adverse Events Related to Typical PD Therapy by SOC and Preferred Term
14.3.1.1.9	Serious Treatment-Emergent Adverse Events Related to Another Baxter Product by SOC and Preferred Term
14.3.1.1.10	Treatment-Emergent Adverse Events Leading to Withdrawal by SOC and Preferred Term
14.3.1.1.11	Treatment-Emergent Adverse Events Leading to Death by SOC and Preferred Term

14.3.1.1.12	Treatment-Emergent Adverse Events of Special Interest by SOC and Preferred Term
14.3.1.1.13	Treatment-Emergent Adverse Events in $\geq 5\%$ of Patients by SOC and Preferred Term
14.3.1.3.1	Treatment-Emergent Adverse Events by SOC, Preferred Term, and Severity
14.3.1.3.2	Treatment-Emergent Adverse Events by SOC, Preferred Term, and Relationship with Study Device
14.3.1.3.3	Treatment-Emergent Adverse Events by SOC, Preferred Term, and Relationship with Typical PD Therapy
14.3.1.3.4	Treatment-Emergent Adverse Events by SOC, Preferred Term, and Relationship with Another Baxter Product
14.3.4.1	Hematology Laboratory Summary at Baseline
14.3.4.2	Chemistry Laboratory Summary at Baseline
14.3.5.1	Vital Signs Summary and Change from Baseline
14.3.6.1	Summary of Device Deficiencies

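### The SAP replaces the protocol's pre-to-post-treatment vital-sign change with change from baseline without declaring it, and the stated eCRF schedule holds neither the pre/post pairs nor post-baseline temperature

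*SAP*

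**What the plan says.** **Planned analysis.** Protocol 10.6, with the same text in the synopsis, summarises blood pressure, pulse and temperature at all recorded timepoints and "also for change from pre-to post treatment for all post Baseline timepoints". SAP 14.3.3 states that systolic and diastolic pressure, pulse rate and temperature "will be summarized descriptively at each time-point using both absolute values and change from baseline for all post-baseline timepoints". The only vital-sign table in SAP 17 is 14.3.5.1, "Vital Signs Summary and Change from Baseline".

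**Declaration of changes.** Protocol 10.1 says: "Any changes to the statistical methods described in the protocol will be documented in the SAP". SAP 12 says: "There have been no changes from the planned analyses in the protocol".

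**Collection.** Protocol 8.5 lists, for each treatment day: "Vital signs, before and after each treatment, including seated BP, pulse rate and temperature". Section 8.7 carries the 8.5 assessments into Visits 2, 3 and 4. Section 6.4 says: "Vital signs (BP and pulse rate) will be recorded on the eCRF at Screening, Study Visit 2, Study Visit 3, Study Visit 4", and adds the End-of-Study Visit. Footnote j of Appendix 1 repeats this. The vital-signs row of Appendix 1 is marked at those same visits and is blank under Baseline Period and Each Treatment Day. The SAP's own Appendix 1 reproduces the row and the footnote.

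**Baseline.** SAP 14.3.3 takes Baseline Period measurements as baseline and falls back to Screening values when they are missing.

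**The concern.** The two analyses answer different questions. A pre-to-post change describes what happens to a patient's blood pressure, pulse and temperature over a treatment session. A change from baseline describes drift over weeks, and one cannot stand in for the other. The study has no control group, so within-patient change is the main vital-sign contrast it can offer, and vital signs are a named component of the secondary safety endpoint. If the SAP is followed as written, the within-session summary is not reported and SAP 12 tells the reader that nothing was altered.

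The collection text adds a second problem. Both documents promise a temperature summary, and the protocol promises paired readings, yet the sections that say what goes on the eCRF mention neither. A programmer working from 6.4 and Appendix 1 would have no stated source for them.

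**Working it through.** The documents give no figure to reproduce on this point, so the check is a comparison of sections followed by a count.

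**Step 1: same protocol version?** The SAP says it is based on Amendment 6 dated 01NOV2019. The protocol's most recent amendment date is 2019 NOV 01. A version difference does not explain the discrepancy.

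**Step 2: is the pre-to-post change anywhere in the SAP?** It is not in 14.3.3 or the table list. SAP 16.3 also keeps the first available result when several are collected at a post-baseline visit, so at most one reading of a same-day pair would enter the table.

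**Step 3: what does the stated eCRF schedule support?** Inputs are protocol 6.4, Appendix 1 (row and footnote j) and the baseline rule in SAP 14.3.3. The post-baseline eCRF timepoints are Visits 2, 3, 4 and End of Study: 3 + 1 = 4.

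| Analysis | BP | Pulse | Temperature |
|---|---|---|---|
| Pre-to-post change (protocol 10.6) | no pair scheduled | no pair scheduled | no pair scheduled |
| Change from a Baseline Period value | no vital-signs entry scheduled | no vital-signs entry scheduled | no vital-signs entry scheduled |
| Change from Screening (SAP fallback) | 4 of 4 timepoints | 4 of 4 timepoints | 0 of 4 timepoints |

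The pre-to-post analysis is therefore supported for 0 of 3 measures. The SAP's change from baseline is supported for blood pressure and pulse, but only through the fallback. Temperature is taken at Screening under protocol 8.2 but is not named among the eCRF vital signs at any visit.

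**Step 4: is another data path named?** The eDiary items in protocol 5.9 and SAP 11.1 do not mention vital signs, nor do the machine observations in Appendix 1 footnote t. The eDiary list is open-ended, so capture there is possible but unspecified. Daily pre- and post-dialysis weight, by contrast, has its own Appendix 1 row with a mark under Each Treatment Day.

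**Step 5: how many pairs does 8.5 imply?** With one treatment a day, 12 weeks × 7 days = 84 pairs per completer, and 84 × 30 target completers = 2,520. If only Visits 2-4 yielded pairs, it would be 3 per completer and 3 × 30 = 90. The larger figure is an upper-end illustration for 30 completers: it assumes that 8.5 governs and that no treatment is missed, and it leaves out Safety Set patients who do not complete.

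**The case against.** **The protocol phrase may mean something else.** End of Study is a post-baseline vital-sign timepoint 5-10 days after the last study treatment, with no session to pair. Pre-to-post treatment could then mean before study treatment against later, which is roughly what the SAP does. This has some force, but the other reading is better supported. Section 8.5 asks for readings before and after each treatment, which is the data a within-session change needs. Protocol 10.6 also uses change from Baseline by name for total Kt/V, so that term was available had it been meant for vital signs.

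**The SAP's analysis is feasible.** A reader might infer that the eCRF supports neither analysis, or that the vital-sign baseline is undefined. The documents do not support that. The Screening fallback is already in SAP 14.3.3, and blood pressure and pulse are on the eCRF at Screening and all four later timepoints. Protocol 8.4 also has both evaluated in the Baseline Period investigator assessment, although eCRF entry is not stated.

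**The eCRF itself is not available.** A reader might also infer that temperature will not be collected, or that its table will be empty. That goes too far. Section 8.5 requires temperature, 8.7 extends it to Visits 2-4, 8.10 lists vital signs at End of Study without restriction, and 11.8 says all clinical data are captured electronically. What is shown is a conflict between sections about what is recorded. Likewise, SAP 14.3.3 does not exclude daily readings, since it summarises each time-point; what it lacks is the pairing.

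**The impact is small.** The study is descriptive, and protocol 10.2 says: "A formal sample size calculation was not performed". Under protocol 7.2, vital-sign abnormalities that are clinically significant, need intervention or lead to discontinuation are recorded as adverse events. This stands, and it limits how much weight the point can carry.

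**Conclusion.** The point holds in two parts.

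- **Undeclared departure.** The SAP omits the pre-to-post-treatment change planned in the protocol, gives change from baseline in its place, and states that nothing changed. This rests on the within-session reading of protocol 10.6, which 8.5 favours. Confidence is high.
- **Conflict over capture.** Protocol 8.5 and 8.7 require paired readings including temperature; 6.4, footnote j and the vital-signs row list only blood pressure and pulse at five visits. As stated, the eCRF schedule supports the pre-to-post change for 0 of 3 measures and temperature at 0 of 4 post-baseline timepoints. This rests on taking the parenthesis in 6.4 as the full list of measures, so confidence is lower.

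The conclusion does not extend to blood pressure and pulse change from baseline, which is computable at 4 of 4 timepoints. It affects one descriptive summary within a secondary safety endpoint, should be corrected before the tables are produced, and leaves the primary endpoints untouched.

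**What to change.** 1. Add the pre-to-post-treatment change from the 8.5 readings to SAP 14.3.3 and to the table list, alongside change from baseline. Compute a mean change per patient, then summarise across patients, so that patients with more treatments do not dominate. State that the first-available-result rule in SAP 16.3 does not apply to the pair.
2. If the summary is to be dropped, for example because the pairs are not in the database, say so in SAP 12 with the reason.
3. Reconcile protocol 6.4, 8.5 and Appendix 1 (row and footnote j), and the SAP's copy of that appendix, on where temperature and the daily pre/post readings are captured. If temperature has no post-baseline source, SAP 14.3.3 should not promise its summary.

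The Screening fallback needs no change. The cost is SAP wording, one more descriptive table and a data-capture clarification.

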14.3.4 Laboratory Results

The following laboratory results (and corresponding changes from baseline, if applicable) will be summarized descriptively using n, mean, standard deviation, minimum, median, and maximum for all timepoints taken:

- Hematology:
 - Complete blood count with differential from serum blood draw
 - White cell count with differential from PD Effluent
 - Cell culture from PD Effluent

- Chemistry:
 - Chemistry profile from blood draw consisting of:
 - Glucose
 - Calcium
 - Albumin
 - Total protein
 - Sodium
 - Potassium
 - Bicarbonate
 - Chloride
 - Creatinine
 - Blood urea nitrogen
 - Alkaline phosphatase
 - Alanine aminotransferase
 - Aspartate amino transferase
 - Bilirubin
 - Phosphorus
 - Creatinine from 24-hour PD Effluent collection
 - Urea Nitrogen from 24-hour PD Effluent collection
 - Creatinine from 24-hour urine collection
 - Urea Nitrogen from 24-hour urine collection

If a patient had re-enrolled, all data gathered from all laboratory tests will be summarized.

For all laboratory values, the measurement taken at screening is considered baseline except for the Creatinine and Urea Nitrogen from Blood Draw; these two parameters will use their measurements taken during the Baseline Period as baseline.

14.3.5 Feed Water Analysis

The results of the feed water analysis from the patients' home will be analyzed descriptively using frequencies and percentages of those that meet specifications vs those that do not. A test will be considered meeting specifications if all of the following parameters fall within the specified limits:

Parameter	Maximum Limit
Aluminum	0.3 mg/L
Antimony	0.006 mg/L
Arsenic	0.01 mg/L
Barium	2 mg/L
Beryllium	0.004 mg/L
Cadmium	0.005 mg/L
Chromium	0.1 mg/L
Cobalt	0.025 mg/L
Copper	1.3 mg/L
E. Coli Units	<1 CFU/mL
Fluoride	2 mg/L
Heterotrophic Plate Count	<500 CFU/mL
Lead	0.015 mg/L
Mercury	0.002 mg/L
Nickel	0.02 mg/L
Nitrate (measured as Nitrogen)	10 mg/L
Selenium	0.05 mg/L
Silver	0.1 mg/L
Thallium	0.002 mg/L
Total Coliform Unit	<1 CFU/mL
Turbidity	3 NTU
Zinc	5 mg/L

If any of the above parameters fall outside the limits, then the particular test is considered not meeting specifications. If any of the above parameters were not tested, then the particular test is considered missing. These tests will be performed at [REDACTED].

There will be three summaries of these data: one based on initial values, one based on retest values (as mandated per decision trees), and one based on the most recent test values. These three summaries will be done on a combination of all visits and individually for each of the visits.

In addition to the above, there will be two additional tables detailing the feed water analysis. The first will show the test results (met vs did not meet specifications) for each of the individual parameters, and the second will be a descriptive summary (n, mean,

standard deviation, minimum, median, and maximum) of the results of each of the individual parameters.

If a patient had re-enrolled, all data will be used in this analysis. The test results will also be listed. Patient's age, sex, race, and weight at baseline will not be shown for this listing. This listing will include all enrolled patients.

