### **4.2 Inclusion Criteria**

Each patient must meet ALL of the following criteria to be enrolled in this study:

1. Patient is 18 years or older.
  2. Patient with ESRD receiving PD therapy, and who is already trained and regularly using the AMIA or HomeChoice APD Cycler with Dianeal PD Solution for at least 12 weeks.
- 
- 

- 
3. Patient is receiving or willing and able to use Dianeal Low Calcium (2.5 mEq/L) PD prescriptive regimen at study treatment initiation per Investigator's assessment.
  4. Patient demonstrates adequate PD therapy with clinical euvolemia as assessed by the Investigator with a total  $Kt/V_{urea}$  of a minimum of 1.7 within 45 days of Screening, or measured at Screening. If a total  $Kt/V_{urea}$  is not available within 45 days of Screening, it will be measured at Screening.
  5. Investigator assesses that, with appropriate training, the patient will be able to successfully manage his/her dialysis treatments with the AMIA APD Solution Generation System.
  6. Patient is available and is willing to complete training on the AMIA APD Solution Generation System.
  7. Patient and home environment are deemed suitable for treatment with the AMIA APD Solution Generation System, while in the home.
  8. Home electrical and water assessments meet suitability criteria for the AMIA APD Solution Generation System.
  9. The patient's home has suitable wireless connection or patient is willing to allow installation of suitable wireless connection.
  10. Patient and/or care partner (if participating) (See Section 5.4.1) is able to read and understand English, and provide informed consent after an explanation of the proposed study. If the patient does not read and understand English, patient may still participate if he/she has a co-residing care partner who reads and understands English, assessed as adequate by the PI.
  11. Women of childbearing potential (not menopausal or surgically sterile) must not be pregnant. Serum qualitative and quantitative pregnancy test will be done within 14 days prior to initiation of study product.
    - If qualitative serum  $\beta$ -hCG results are positive, repeat quantitative serum pregnancy test in 48 hours.
    - If quantitative serum  $\beta$ -hCG levels show clinically significant rise within 48 hours, serum progesterone level should be taken. Serum progesterone > 5 ng/mL will exclude a patient from the study.
- 
-

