#### **4.4 Home Assessment and Installation**

During the Screening Period, all consented patients will have a home assessment to confirm the patient's home environment is suitable for the study. The patient's home environment must meet the AMIA APD Solution Generation System requirements to be eligible for enrollment (Refer to AMIA APD Solution Generation System Patient Guide for details of the system requirements). To provide schedule flexibility for the consented patient, Baxter Service or its designee may begin the home installation process during the Screening Period. System installation and product water from the WD (pre-sterilizing filters) testing are expected to take approximately two weeks. This will ensure the system is ready for activation after the patient completes his/her required in-center training on the AMIA APD Solution Generation System.

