### **6.5.8 Water and Dialysate Sampling Analysis**

Feed water used to supply the WD will be collected by Baxter personnel and sent for analysis during the home assessment process and again at the de-installation visit. Feed water shall not exceed the chemical or biological contaminant levels as stated in the AMIA APD Solution Generation System feed water specification and Feed Water Sampling at Installation for PoC APD. The product water from the WD (pre-sterilizing filters) shall conform to ISO 13959 for microbiological (including endotoxin) and chemical contamination, and the water in the holding bag (post-sterilizing filters) shall not exceed 0 CFU/mL for bacteria (no growth) and be < 0.03 EU/mL for endotoxins, consistent with Dianeal specifications for sterility. Product water shall not exceed the nitrate contamination limit of 2 mg/L. Sampling for product water testing for microbiological and chemical contamination may be done on different days within the allocated window.

The Sponsor or its designee will train the site nurses responsible for collecting the water and dialysate samples during the study. Instructions will be provided in the study training materials. Standardized recovery methods and controls will be incorporated into the testing protocol(s). Central laboratories will be used for all water and dialysate testing.

---

Sample results will be sent to the study sites and Sponsor for real time review and action (if appropriate). Observations and decisions regarding corrective measures (e.g., re-culture and/or disinfection of the WD) will be based on the organism growing and on whether bacterial or endotoxin levels exceed the specified guidelines. An internal Sponsor Committee will also review study wide results on a bi-weekly basis, at a minimum, to search for trends and to action appropriately.

Analysis of water will be performed on samples obtained as follows.

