#### **6.5.8.1 Chemical Contaminants**

##### **Feed Water**

Samples of feed water will be collected by Baxter personnel or designees and tested for chemical contaminants from each study site during site feasibility, prior to AMIA APD Solution Generation System installations at the site, according to limits stated in the AMIA APD Solution Generation System feed water specification. Samples will also be collected from feed water at patients' homes during home assessments while consented patients are in the Screening Period and at de-installation.

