7. DISPOSITION

7.1 Patient Disposition

Patient disposition will be summarized and will include:

- Number of patients who signed informed consent
- Number of patients enrolled (defined as having a home installation and meeting all eligibility criteria)
- Number of patients treated
- Number of patients in the Safety Set
- Number of patients who completed the study
- Number of patients who discontinued (withdrew early) from the study and subsequently re-enrolled. These patients will also be summarized by primary reason for withdrawal from the study. The percentages associated with each reason for early withdrawal will have the total number of patients who withdrew early and re-enrolled as the denominator
- Number of patients who discontinued and did not subsequently re-enroll. The percentage associated with this will be the number of patients who withdrew and did not re-enroll.

Patients who withdrew early from the study will be listed, and the listing will include the number of days that the patient remained in the study, the primary reason from withdrawal, and whether the patient re-enrolled.

All disposition tables and listings will be based on the set of all patients who signed informed consent.

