14.3 Other Safety Data

14.3.1 General

Unless otherwise specified, tables, listings, and figures will be based on the Safety Set.

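### SAP 14.3.5 reports Screening feed water only for patients admitted partly on that result, so homes that finally fail appear in no feed-water table or listing

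*SAP*

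**What the plan says.** **Feed water decides entry.** Inclusion criterion 8 in protocol 4.2 reads "Home electrical and water assessments meet suitability criteria for the AMIA APD Solution Generation System". Protocol 4.4 says the home must meet the system "requirements to be eligible for enrollment". Protocol 6.5.8 adds: "Feed water shall not exceed the chemical or biological contaminant levels as stated in the AMIA APD Solution Generation System feed water specification". Protocol 9.2 rules out waivers.

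**When homes are sampled.** Under protocol 6.5.8.1, patients' homes are sampled "while consented patients are in the Screening Period and at de-installation". Each home that is installed thus has two scheduled tests, and a home that fails for good has only the Screening test(s).

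**Who is reported.** SAP 14.3.5 names no population for its tables, so the default in SAP 14.3.1 applies: "Unless otherwise specified, tables, listings, and figures will be based on the Safety Set". The Safety Set (SAP 7.2) requires at least one study treatment and at least one primary-endpoint measurement. For the listing, SAP 14.3.5 says "This listing will include all enrolled patients". SAP 7.1 explains what enrolled means: "Number of patients enrolled (defined as having a home installation and meeting all eligibility criteria".

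**What is summarised.** There are three pass/fail summaries, based on initial, retest and most-recent values. On visits the SAP says: "These three summaries will be done on a combination of all visits and individually for each of the visits".

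**Screen failures.** Protocol 8.2 item 14 requires the reason for each screen failure to be recorded. SAP 7.1 lists neither a screen-failure count nor a breakdown by reason, and no title in SAP 17 names screen failures.

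**The concern.** The feed-water outputs are conditioned on the result they report. A patient reaches the tables or the listing only after the home has cleared the feed-water check, and the homes that did not clear it are left out of both. A Screening pass rate on that basis says little about how often home feed water is acceptable.

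The combined display adds a second problem. For dialysis solution, product water and holding-bag water, the visits being combined are repeated in-study measurements. For feed water, the two scheduled visits are the entry check and the de-installation test, so the combination averages a selection criterion with an outcome.

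At stake is a reported percentage, and the reader's ability to see what share of consented homes the system could be used in.

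**Working it through.** The plan states no feed-water pass rate, so there is no figure to reproduce. The checks use plain proportions. The documents give no failure, retest or de-installation rates, so every rate below is an assumption shown over a range.

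**1. Trace a home that finally fails**

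| Step | Source | Result |
|---|---|---|
| Feed water sampled after consent | Protocol 6.5.8.1 | Result exists |
| Water criterion not met | Protocol 4.2 item 8, 4.4 | Not eligible |
| Classification | SAP 7.3 | Screen failure |
| Enrolled? | SAP 7.1 definition | No, so not in Listing 16.2.11.3 |
| Safety Set? | SAP 7.2 | No, never treated, so not in Tables 14.3.7.7 to 14.3.7.9 |
| Disposition | SAP 7.1, all consented patients | Counted as consented, with no reason shown |

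**2. Most-recent value at Screening.** Assume that the SAP 14.3.5 limits are those used for eligibility, that there are no entry deviations, and that each patient has one Screening episode. Every admitted home then has a passing last Screening test, so the rate is 100% whatever share of consented homes failed.

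**3. Most-recent value, visits combined.** With n_S Screening and n_D de-installation tests, Screening at 100% and de-installation at p:

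combined = (n_S + n_D × p) / (n_S + n_D), which is (1 + p)/2 when n_S = n_D.

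| De-installation p | Equal numbers | 50 Screening, 30 de-installation (assumed) |
|---|---|---|
| 95% | 97.5% | 98.1% |
| 90% | 95.0% | 96.2% |
| 80% | 90.0% | 92.5% |
| 70% | 85.0% | 88.8% |

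For example, (50 + 30 × 0.80)/80 = 74/80 = 92.5%.

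**4. Initial value at Screening.** Let f be the share of consented homes failing the first test, and r the share of those failures admitted after a passing retest. Then:

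rate among admitted = (1 − f) / [(1 − f) + f × r]; rate among all consented homes tested = 1 − f.

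| f | r = 0 | r = 0.25 | r = 0.5 | r = 0.75 | r = 1 | All consented |
|---|---|---|---|---|---|---|
| 10% | 100% | 97.3% | 94.7% | 92.3% | 90.0% | 90.0% |
| 20% | 100% | 94.1% | 88.9% | 84.2% | 80.0% | 80.0% |

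For f = 20% and r = 0.5: 0.80/(0.80 + 0.10) = 88.9%, against 80.0% in all consented homes. The two agree only when r = 1.

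**5. Effect of restoring the failed homes.** With n admitted homes and k that finally failed, the most-recent Screening rate becomes n/(n + k). The values of n are the SAP's 30 target completers and 50 maximum enrolled; k is assumed.

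| n | k = 3 | k = 6 | k = 10 |
|---|---|---|---|
| 30 | 90.9% | 83.3% | 75.0% |
| 50 | 94.3% | 89.3% | 83.3% |

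**The case against.** The best defence is that most of what a reader needs is already planned, and that feed water is a side issue. Four stronger readings are tempting, and the documents do not support them.

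- **That every Screening feed-water rate is near 100%.** This is true only of the most-recent-value summary. A home that fails first and is admitted after a retest counts as a failure in the initial-value summary and appears in the listing. The (1+p)/2 formula carries the same limit.
- **That combining visits hides the de-installation result.** It does not, because the sentence that orders the combination also orders each visit separately. SAP 14.3.5 does not, however, state a by-visit display for its two individual-parameter tables.
- **That failed homes vanish from the report.** Disposition covers all consented patients, so these homes sit in the gap between consented and enrolled. What is missing is the reason: a feed-water failure cannot be told apart from any other screen failure.
- **That the primary safety result is biased.** Feed water is neither a primary nor a secondary endpoint; the SAP places it under other safety data. Product water can be measured only where a system is installed, and limiting the study to suitable homes is its declared population.

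A further objection has force. The feed-water specification and the feed-water decision tree are external documents. It cannot be confirmed that the SAP limits equal the eligibility limits, or that every exceedance bars entry. SAP 14.3.5 also uses all data from re-enrolled patients, so an earlier failing test could enter for someone screened twice. The 100% figure is therefore conditional. The objection does not put the finally failing homes back into any feed-water output, and it does not make the combined percentage interpretable.

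**Conclusion.** The point holds as a reporting defect of limited reach. Homes that finally fail the feed-water check appear in no feed-water table or listing, and the plan does not show how many consented homes were lost for that reason.

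The most-recent Screening pass rate among admitted patients is 100% by construction if three things hold: the SAP limits match the eligibility specification, there are no entry deviations, and no rescreened patient brings in an earlier failure. On those terms, and with equal numbers at both visits, the combined figure overstates the de-installation rate by (1 − p)/2, which is 5 percentage points at p = 90% and 10 at p = 80%. The initial-value rate is biased upward by an amount that depends on how many first failures are admitted: 8.9 points (88.9% against 80.0%) if 20% fail first and half of those are admitted.

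These sizes are illustrations, since the documents give none of the underlying rates. No primary or secondary result changes.

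**What to change.** 1. In SAP 14.3.5, base the Screening feed-water tables and listing on all consented patients whose home feed water was tested. Show the numbers that passed at first test, passed on retest, and were excluded.
2. Keep the planned by-visit de-installation result in the Safety Set, and say so in the section.
3. Drop the combination of Screening with de-installation. If it is kept, footnote that passing the Screening test was a condition of entry.
4. In SAP 7.1, add screen failures by recorded reason, with feed water and home suitability identifiable.
5. State in SAP 14.3.5 whether its limits are the ones used for eligibility.

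The cost is SAP wording and minor table work. The Screening samples and the screen-failure reasons are already collected, so no sampling, visit or patient burden is added. The one drawback for the sponsor is a Screening rate that may look less favourable.
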